PROTOCOL TITLE:

Life Enhancing Activities for Family Caregivers (LEAF) 2.0

PRINCIPAL INVESTIGATOR:

[name], MPH

Professor || Department of Medical Social Sciences || Northwestern University

Director of Research || Osher Center for Integrative Medicine

Director || BSIS Core, Third Coast Center for AIDS Research

[contact]

[contact]

CO-INVESTIGATORS:

[name]

Research Assistant Professor

Department of Medical Social Sciences || Northwestern University

[contact]

[contact]

[name]

Assistant Professor

Department of Medical Social Sciences || Northwestern University

[contact]

[contact]

VERSION DATE:

December 10, 2020

1.0 Purpose of the study:

The Life Enhancing Activities for Family Caregivers (LEAF) 2.0 Course is an intervention containing a series of positive emotion skills for the family caregivers of individuals with Alzheimer's Disease (AD) (1R01AG05613-01). LEAF 2.0 builds upon the LEAF 1.0 intervention (R01NR014435) in that it specifically targets positive emotion, focuses on the caregiver, is a multicomponent intervention that offers an array of skills, and offers online delivery (either facilitated or self-guided) which makes the intervention accessible and convenient.

We will conduct a 3-arm randomized controlled trial with 500 total caregivers of individuals with AD. 200 will be assigned to the web-based facilitated LEAF program (Condition 1), 200 assigned to the web-based self-guided LEAF program (Condition 2), and 100 will be assigned to the emotion reporting waitlist-control condition (Condition 3) with crossover to the either the facilitated version or to the self-guided version; 50 in each condition, respectively. The crossovers take place after approximately 7 months into the study. Participation in the study lasts about 14 months.

LEAF 2.0's three main aims are:

Aim 1: To compare the effect of online self-guided and facilitator-guided delivery modes of LEAF to an emotion-reporting control condition on positive affect, depression, anxiety, and perceived stress.

Aim 2: To explore the effects of LEAF on caregiving burden, self-efficacy, positive aspects of caregiving, quality of care, and AD patient quality of life and assess whether these effects on outcomes are mediated by improvements in positive emotion.

Aim 3: To test whether caregiver age, gender, or baseline stress (dementia severity) moderate the effects of the intervention.

2.0 Background / Literature Review / Rationale for the study:

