The co-Investigator is at the UCSF School of Nursing ([name]) and the Project Director ([name]) manages recruitment, phone screening, and the technology orientation at UCSF. [name] is also a study team member, LEAF 2.0 facilitator and is at UCSF.

Northwestern and UCSF will be working collaboratively on this project and we will rely on the Northwestern IRB as the IRB of record. The management of tablets (shipment, technology training, etc.) will take place at Northwestern. We have weekly all-team meetings that include everyone from both sites. Subs-groups also meeting weekly or every other week (e.g. content development or the measures team) to review and discuss relevant topics. The frequency and length of the all-team meeting and sub-group meetings will adapt as the study launches.

NU and UCSF are jointly working towards our recruitment goal of N = 500. There will not be a recruitment distinction between sites, since we are collectively recruiting caregivers nation-wide and there is no in-person contact with participants. All modifications will be jointly discussed between NU-UCSF, but first submitted and approved through the NU IRB (IRB of record). Once changes have been approved through the NU IRB, then we will send the Modification Approval Letter to UCSF for UCSF IRB approval.

7.0 Reliance Agreements/Single IRB:

LEAF 2.0 is a multi-site study with reliance on a single IRB through Northwestern's Social and Behavioral Research Panel. We will be pursuing a reliance agreement with UCSF through SMART IRB. No research activities at UCSF will take place until the submission to modify the study with the reliance agreement is approved by the IRB.

8.0 Procedures Involved:

This study has been registered with clinicaltrials.gov and the NCT number is: **NCT03610698**. The clinicaltrials.gov registration number (NCT) will be listed on the consent forms and recruitment materials and approved by the NU IRB prior to starting recruitment.

Online Pre-Screener Link

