Simple group comparisons for single time points or pre-post comparisons between the facilitated (n=200) and self-guided (n=200) groups will have 80% power to detect effect

sizes of $d=.28$ ($R^2=.019$), below the observed effect sizes for positive emotion, negative emotion, stress, depression, and anxiety in our previous LEAF trial. Comparisons between the wait-list control group ($n=100$) and the LEAF interventions individually ($n=200$) or taken together ($n=400$) will have 80% power to detect effect sizes of $d=.34$ ($R^2=.029$) and $d=.31$ ($R^2=.024$), respectively.

Our design of seven time points and 500 individuals exceed established minimums for detecting predictors of individual differences¹⁰⁸ and for detecting associations between parallel growth processes.¹⁰⁹ Power for these models was estimated by Monte Carlo simulation to account for our longitudinal experimental design. Effects of observed predictors (i.e., LEAF group, Aim 1) had 80% power for effects of $d=.27$ ($R^2=.018$). Parallel growth curves showed 80% power for slope correlations of $r=.14$ ($R^2=.019$), and comparable power for indirect effects of ($r=.15$, $R^2=.021$), consistent with previous work on mediational power.¹¹⁰

Missing Data

Although our previous test of LEAF showed high adherence rates and minimal dropout, all longitudinal analyses must plan for missing data. All proposed models will be fit with full information maximum likelihood, which yields unbiased parameter estimation under common missing data mechanisms. Multiple imputation will be used in any cases where covariates predict missingness but would otherwise not be included in proposed models.

9.0 Incomplete Disclosure or Deception:

N/A

10.0 Recruitment Methods:

We plan to recruit participants over the period of 42 months. Recruitment efforts will target the 2 major national organizations servicing patients with dementia and their caregivers: 1) the Alzheimer's Association and 2) the Family Caregiver Alliance: National Center on Caregiving.

We will also use print, radio, and websites at the national and local level of these organizations to access a geographically and age diverse cohort. Subjects will also be recruited from the Northwestern University Alzheimer's Center, the University of California San Francisco Memory and Aging Center, The New Normal, and the NUCATS recruitment tool. We will also recruit on Alzheimer's-related websites that give us permission to post.

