13.0 Audio/Video Recording

The facilitator-guided LEAF sessions will be digitally video- and audio-recorded using a secure, encrypted internet connection on a password-protected platform such as Zoom. Each participant in the facilitator-guided intervention will have approximately 6 audio-recorded sessions (one for each intervention session, 6 total), recorded for quality assurance purposes and to evaluate the intervention. These recordings will be securely stored on Northwestern password-protected servers, accessible only to IRB-approved staff. The videos will be labeled by Study ID.

Fidelity will be assessed qualitatively with a checklist and comments for each component of a session as we have done in LEAF 1.0 and other face-to-face delivery of the intervention. Sessions will be reviewed by the project director to assess adherence to the protocol, delivery, facilitator/participant rapport, and session flow. All sessions of the first three participants (for each facilitator) will be reviewed immediately. This will be followed by regular (weekly, then monthly) reviews of selected sessions thereafter.

14.0 Potential Benefits to Participants:

There is no guaranteed benefit from participating in LEAF 2.0, however participants might enjoy the skills taught in LEAF and continue practicing them beyond the online course e.g. keeping a gratitude journal, completing everyday chores mindfully, or listening to a breath awareness meditation recording. Participants may gain mindfulness skills, regularly capitalize on positive events, or use positive reappraisal to reassess daily stressors. Even after completing the course, participants are encouraged to keep using their favorite skills, whether formally through the website and/or journaling about their experiences, or informally in their everyday lives.

On a broader scale, we predict that the skills taught in LEAF 2.0 may help family caregivers of dementia patients increase their positive affect and lower depression, anxiety, and perceived stress. We will explore the effects of this intervention on caregiving burden, caregiving efficacy, positive aspects of caregiving, quality of care, and AD patient quality of life. We will assess whether these effects on outcomes are mediated by improvements in positive emotion.

15.0 Risks to Participants:

Minimal Risk; Possible discomfort while interacting with the LEAF platform

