Official title: Randomized Trial of a Technology-based Positive Emotion Intervention for Informal Caregivers of Individuals With Alzheimer's Disease

Brief title: Life Enhancing Activities for Family Caregivers (LEAF 2.0)

NCT#: NCT03610698

Date: 10/20/2025

Demographic characteristics, including age, gender, race, ethnicity, income, education, and residence were summarized for the sample as a whole, and by intervention group (Facilitated Intervention, Self-Guided Intervention, and combined Control). Differences between groups were calculated using one-way ANOVA for continuous variables and Chi-squared tests for categorical variables; Fisher's exact tests were used when required by the distribution. Baseline scores for each outcome were compared across the three groups using ANOVA and Kruskal-Wallis tests, depending on the distribution of the data.

Change over time and differences within- and between- intervention groups were assessed using mixed effects linear regression models. Time (baseline, post-intervention, follow-up 1 and follow-up 2) was treated categorically to allow for slope estimates to differ between consecutive timepoints. Models included a random effect for intercept and time. From these models, within-group and between-group differences across intervention groups (Facilitated, Self-Guided, and Control) were estimated between baseline and each follow-up time point (post, FU1, and FU2) using least square means estimates. Effect sizes were calculated to compare change over time across intervention groups.

Lastly, we calculated the number of sessions/weeks completed for each participant during their intervention period to assess how the number of weeks completed moderate the effect of intervention on change in each outcome. We used mixed effects linear regression models including time, intervention group, and usage (none, some, or all sessions) to estimate the change from baseline to each follow-up (post, FU1, and FU2) in both intervention groups, and test for significant change both within and across intervention groups (facilitated, self-guided).

All analyses were performed using SAS v. 9.4; p-values were considered significant at $p < 0.05$.

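### Neither document names a primary outcome, primary contrast, primary time point or multiplicity rule, so p < 0.05 applies alike to about 24 Aim 1 comparisons with control

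*SAP*

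**What the plan says.** - **Decision rule.** The SAP's last sentence covers all analyses: "p-values were considered significant at $p < 0.05". It gives no hierarchy and no adjustment.
- **Outcomes and contrasts.** Aim 1 (protocol section 1.0) compares self-guided and "facilitator-guided delivery modes of LEAF to an emotion-reporting control condition on positive affect, depression, anxiety, and perceived stress". Protocol section 14.0 repeats the same four outcomes as its prediction, that LEAF may help caregivers "increase their positive affect and lower depression, anxiety, and perceived stress", and treats the caregiving and patient outcomes as exploratory. The four are not ranked, nor are the two delivery modes.
- **Time points.** In the SAP's mixed-model paragraph, within-group and between-group differences "were estimated between baseline and each follow-up time point (post, FU1, and FU2"). None comes first.
- **Outcome list.** The SAP has none. Its usage analysis asks how sessions completed "moderate the effect of intervention on change in each outcome". The protocol's Table of Measures gives two possible positive-affect instruments at every time point, the DES and PROMIS Positive Affect 15a, and chooses neither.
- **Power.** In protocol section 8.0 (Power), comparisons of control with the "LEAF interventions individually ($n=200$) or taken together ($n=400$) will have 80% power to detect effect sizes of $d=.34" (one arm) and d=.31 (pooled). Facilitated against self-guided has d=.28. A separate simulation statement reads: "Effects of observed predictors (i.e., LEAF group, Aim 1) had 80% power for effects of $d=.27".
- **Registration.** Protocol section 8.0: "This study has been registered with clinicaltrials.gov". That record is not part of these documents.

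**The concern.** Aim 1 asks whether either LEAF mode does better than emotion reporting. The documents do not say which result answers that question. A report that follows the SAP could present any Aim 1 comparison below 0.05 as an effect of LEAF, and a reader could not tell a planned finding from a selected one. With many correlated tests at 0.05 each, the chance that at least one is falsely significant is well above 5%.

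**Working it through.** **1. The plan's own figures.** Detectable d = (z for alpha + z for power) x sqrt(1/n1 + 1/n2), with 1.960 + 0.842 = 2.802 for two-sided 0.05 and 80% power.

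- 200 v 200: 2.802 x sqrt(.0100) = .280 (t-test .281; stated .28)
- 200 v 100: 2.802 x sqrt(.0150) = .343 (t-test .344; stated .34)
- 400 v 100: 2.802 x sqrt(.0125) = .313 (t-test .314; stated .31)

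All three reproduce at one two-sided test at 0.05, so they make no allowance for multiplicity. One-sided testing would give about 87% power and does not match. The simulated d=.27 for Aim 1 cannot be checked, because its inputs are not given.

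**2. Number of tests.** 2 contrasts with control x 4 outcomes x 3 follow-ups = 24. Alternatives:

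- 5 instruments x 2 x 3 = 30, if both positive-affect instruments are tested
- 4 x 2 = 8, if Aim 1 means one longitudinal effect per outcome and contrast, as the d=.27 sentence may intend
- 2 x 3 = 6, for one outcome at three follow-ups
- 2, for one outcome at one time point

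These counts leave out facilitated v self-guided, pooled LEAF v control, within-group, usage and Aim 2 tests.

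**3. Error rates with no true effect.** The documents give no correlations, so these are assumed: .3 to .9 between outcomes and .5 to .9 between follow-ups (changes sharing one baseline correlate .5 under compound symmetry). The setup was normal change scores, z tests, arms 200/200/100 and at least 200,000 replicates per setting. The shared control arm makes the two contrasts correlate (1/100) / (1/200 + 1/100) = .67. For 30 tests, the two positive-affect instruments were assumed to correlate .7 to .9.

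| Tests | At least one false significant result | At least one favouring LEAF |
|---|---|---|
| 24 | 24-58% | 12-31% |
| 30 | 26-63% | 13-35% |
| 8 | 15-28% | 8-14% |
| 6 | 14-21% | 7-10% |
| 2 | 8% | 4% |
| 1 | 5% | 2.5% |

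With Holm over the 24 tests, the rates are about 2-4% and 1-2%.

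**4. Power cost, one LEAF arm v control (t-test, Bonferroni).**

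| Share of planned n analysed | Tests | Detectable d | Power at d=.34 |
|---|---|---|---|
| 100% | 1 | .34 | 79% |
| 100% | 2 | .38 | 70% |
| 100% | 8 | .44 | 51% |
| 100% | 24 | .48 | 37% |
| 90% | 1 | .36 | 75% |
| 90% | 24 | .51 | 32% |
| 80% | 1 | .39 | 70% |
| 80% | 24 | .54 | 27% |

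The reduced-n rows matter because the power section applies no dropout and protocol section 10.0 reports recruitment below target.

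**The case against.** The strongest reply is that the registration may name a primary outcome and time frame. If it does, 12-31% no longer describes the trial: two contrasts remain, at about 8% and 4%, and the remedy is mostly to carry that choice into the SAP. This stands as a limit on the finding. A reader might infer that the trial has no primary outcome at all, but these two documents cannot show that.

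The documents do impose some order. Aim 1 names comparisons with control and four outcomes, and Aim 2 is worded as exploratory. So it would be wrong to say that no contrast is named, or that every instrument in the Table of Measures is an efficacy test. What is missing is a ranking within Aim 1.

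Separate families per outcome or per delivery mode would be defensible, and the SAP also reports effect sizes. It states no success rule either, so a reader who infers that one p-value below 0.05 formally declares LEAF effective goes beyond the text. The difficulty is that nothing in the text rules out that use.

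The outcomes and follow-ups are correlated, so the independence figure, 1 - .95^24 = 71%, should not be quoted as the error rate. At the highest correlations assumed (.9 and .9), the chance of a false result favouring LEAF is still 12%.

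**Conclusion.** The point holds for these two documents. Applying 0.05 throughout, with nothing in Aim 1 ranked and no adjustment stated, inflates the false-positive rate for the trial's main question. The size depends on the inferred count and the assumed correlations, but the conclusion does not need the count of 24: over 8 tests the chance of at least one false result favouring LEAF is still 8-14%, against 2.5% for one test. The absence of a stated primary choice and multiplicity rule is certain here. The consequence for the trial is less certain, because the registration was not seen.

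**What to change.** Replace the blanket 0.05 rule for claims of efficacy.

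1. If a primary outcome, instrument, contrast or time point was documented before results were seen, for example in the registration or grant, state it in the SAP with its source and date. Base the claim on it, Holm-adjusted if the family holds more than one test.
2. Otherwise, report Holm-adjusted p-values (two-sided familywise 0.05) beside the unadjusted ones for all Aim 1 LEAF-versus-control tests: 24, or 30 with both positive-affect instruments. Label the adjustment post hoc, state the full number of tests, and describe results significant only before adjustment as exploratory.

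Keep the facilitated v self-guided test, and the pooled LEAF v control test if it is run, since the protocol powers both. Report them outside the Aim 1 family as secondary, with 95% confidence intervals and labelled unadjusted. Report within-group and usage analyses as estimates with 95% confidence intervals.

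**Cost.** One added step in SAS and some wording; no new data, and every estimate stays the same. The loss of power is as tabulated for Bonferroni; Holm loses less, but the full-n rows apply only if all planned participants are analysed. Route 1 costs less, and a single documented primary test costs no power. The SAP is dated 10/20/2025 and written in the past tense, so a post hoc adjustment does not restore pre-specification.
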